9 IMMUNOGENICITY ANALYSIS

9.1 Available data

9.1.1 ADA and mADA analysis

9.1.1.1 ADA analysis

Immunogenicity samples will be evaluated in the bridging ADA assay. All samples scoring positive in the ADA assay will be titrated. The $\log_{10}(\text{titer})$ will be reported. The titer represents the last dilution factor of the sample's titration series still scoring positive in the ADA assay. Samples scoring negative in the ADA assay are not titrated and the respective $\log_{10}(\text{titer})$ is reported as $<\log_{10}(\text{Minimal required dilution [MRD]})$ with MRD=96, i.e. $\log_{10}(\text{titer}) < 1.98$. The latter are not included in descriptive statistics on titers.

Subjects will be classified as follows based on the ADA assay results:

- ADA negative: no positive ADA samples at any of the sampling time points
- ADA positive: positive ADA samples at one or more sampling time points
- Inconclusive: no positive ADA samples and drug is present at levels higher than the drug tolerance characteristics of the assay
- Missing: relevant samples are missing

No statement will be made on pre-existing antibody (pre-Ab) positivity pre-dose due the plasma exchange (PE) procedure. During PE (i) pre-Ab present in donor plasma can be transferred to the patient and/or (ii) pre-Ab might be diluted during PE treatment. Since all the patients will be treated with one PE before the first caplacizumab administration, no ADA pre-PE sample will be available to determine the pre-Ab status of the patient.

9.1.1.2 mADA

All positive ADA samples will be further evaluated using the modified ADA (mADA) assay. This assay employs a modified caplacizumab molecule as detection reagent in the bridging format, i.e. caplacizumab-Ala variant. The modification constitutes of a single alanine extension at the C-terminus of caplacizumab. The mADA assay allows detection of drug-induced treatment-emergent (TE) ADA, whereas pre-Ab are not detected. In other words, drug-induced TE ADA will score positive in the mADA assay. Only TE ADA responses with a restricted repertoire, directed against the C-terminal part of the Nanobody (i.e. C-terminal part of the last Nanobody domain), which might be shielded by the presence of the additional alanine on the detector reagent might be left undetected using this mADA assay. All samples scoring positive in the mADA assay will be titrated and reported as $\log_{10}(\text{titer})$ using the same approach as for the ADA assay (see above).

Based on the mADA assay results, subjects will be classified based on pre-Ab and drug-induced TE ADA status as follows:

- Pre-Ab positive – Drug-induced TE ADA negative: all ADA positive samples analyzed in the mADA assay score negative (i)
- Pre-Ab negative – Drug-induced TE ADA positive: all ADA positive samples analyzed in the mADA assay score positive (ii).
- Pre-Ab positive – Drug-induced TE ADA positive: from the ADA positive samples analyzed in the mADA assay, some are positive and some are negative (ii)
- Inconclusive: no positive ADA samples in the mADA assay and drug is present at levels higher than the drug tolerance characteristics of the assay
- Missing: relevant samples are missing

(i) Pre-Ab can originate from the donor plasma introduced during PE procedure or can originate from the patient itself.

(ii) Subjects will be classified as pre-Ab negative, drug-induced TE ADA positive, in case all ADA positive samples analyzed in the mADA assay are positive in the latter assay. However, it cannot be excluded that in addition of the drug-induced TE ADA, pre-Ab against caplacizumab is present in those subjects.

The overall subject classification is based on the ADA and/or mADA assay results, hereafter indicated as “overall subject classification”, and is indicated below:

Overall subject classification:

- Pre-Ab negative – Drug-induced TE ADA negative: no positive ADA samples
- Pre-Ab positive – Drug-induced TE ADA negative: all ADA positive samples analyzed in the mADA assay score negative
- Pre-Ab negative – Drug-induced TE ADA positive: all ADA positive samples analyzed in the mADA assay are positive
- Pre-Ab positive – Drug-induced TE ADA positive: from the ADA positive samples analyzed in the mADA assay, some are positive and some are negative

- Inconclusive: no positive ADA samples and drug is present at levels higher than the drug tolerance characteristics of the assay
- Missing: relevant samples are missing

Subjects classified as ADA negative based on ADA assay results will per default be classified as pre-Ab negative – Drug-induced TE ADA negative.

Given the possible switch to open-label caplacizumab in case of TTP recurrence, subjects will be classified based on the ADA samples available during the DB period, and the OL period separately. For the latter subject classification, the Day 1 visit of the OL treatment period will be used as baseline visit. In addition, patients who switch to open-label caplacizumab after having received double-blind caplacizumab treatment will be classified based on the samples collected during the overall study period. This will be done based on ADA assay results, mADA assay results and for the overall subject classification. Table 5 below provides an overview of the treatment groups for which the incidence in the different classes of the ADA, mADA and overall subject classification will be calculated, and the analysis periods for which this will be done.

Table 5: Overview of treatment groups in the ADA, mADA and overall subject classification

Treatment group	DB period*	OL Caplacizumab period*	Overall study period
Placebo (no OL Caplacizumab)	X		
Caplacizumab (no OL Caplacizumab)	X (i)		
OL Caplacizumab (after Placebo)	X	X (i)	
OL Caplacizumab (after Caplacizumab)	X	X	X (i)
Placebo	Combination of 'Placebo (no OL Caplacizumab)' and 'OL Caplacizumab (after Placebo)'		
Caplacizumab	Combination of 'Caplacizumab (no OL Caplacizumab)' and 'OL Caplacizumab (after Caplacizumab)'		
Caplacizumab Total	Combination of 'Caplacizumab (no OL Caplacizumab)' (DB period), 'OL Caplacizumab (after Placebo)' (OL Caplacizumab period), and 'OL Caplacizumab (after Caplacizumab)' (Overall study period), as indicated by (i)		

* FU samples are included in the DB period if the patients are not switching to OL caplacizumab; in the latter case the FU sample is considered part of the OL Caplacizumab period.

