9.1.2 NAb (neutralizing antibody)

The NAb assay is based on vWF-platelet interaction. As this assay is not sufficiently drug tolerant to detect NAb under treatment, only pre-dose samples (before first caplacizumab administration, i.e. baseline visit) and wash out samples (FU samples) will be analyzed.

All samples scoring positive in the ADA assay at baseline visit or FU samples will be analyzed in the NAb assay. Samples scoring positive in the NAb assay are titrated. The titer per sample is reported as $\log_{10}(\text{titer})$. Samples scoring negative in the NAb assay will be reported as $<\log_{10}(\text{MRD})$ with $\text{MRD}=2.30$ i.e. $\log_{10}(\text{titer})<0.36$. Positive samples for which no titration can be done due to insufficient sample volume will be reported as $>\log_{10}(\text{MRD})$. These positive samples (for which no titration could be done) should be plotted as $\log(\text{MRD})$ equal to 0.36 in the figure.

Subjects will be classified based on their pre-dose status (i.e. baseline visit) and treatment-emergent (TE) status. Subject classification based on NAb is as follows:

- Pre-dose negative, TE negative: no positive samples
- Pre-dose negative, TE positive: negative baseline visit and one or more positive samples post-dose
- Pre-dose positive, TE negative: positive baseline visit and no titer increase post-dose or all samples scoring negative post-dose
- Pre-dose positive, TE positive: positive baseline visit and titer increase post-dose
- Missing: relevant ADA samples are missing

Subjects with no positive NAb samples will be classified as NAb pre-dose negative, TE negative. In listings, samples not evaluated in the NAb assay will be indicated as not analyzed (NA). In graphical presentations, these samples will be presented as negative results.

Given the possible switch to OL Caplacizumab treatment in case of TTP recurrence, subjects will be classified based on the ADA samples available during the DB period, and the OL period, separately. For the latter subject classification, the Day 1 visit of the OL treatment period will be used as baseline visit. Table 6 below provides an overview of the treatment groups for which the incidence in the different classes of the subject classification based on NAb will be calculated, and the analysis periods for which this will be done.

Table 6: Overview of treatment groups in the subject classification based on NAb

Treatment group	DB period*	OL Caplacizumab period*	Overall study period

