Placebo (no OL Caplacizumab)	X		
Caplacizumab (no OL Caplacizumab)	X		
OL Caplacizumab (after Placebo)		X	

CONFIDENTIAL

OL Caplacizumab (after Caplacizumab)			X
Caplacizumab Total	Combination of 'Caplacizumab (no OL Caplacizumab)' (DB period), 'OL Caplacizumab (after Placebo)' (OL Caplacizumab period), and 'OL Caplacizumab (after Caplacizumab)' (Overall study period)		

* Pre-dose and FU samples only.

9.1.3 Alternative NAb (epitope characterization; null variant assay): ADA with neutralizing potential

To detect ADA with potential neutralizing activity during treatment an alternative NAb assay will be used, consisting of the bridging ADA assay in which an altered caplacizumab molecule (i.e. caplacizumab with mutated complementary determining region [CDR] regions) is added in excess to capture all non-CDR binding ADA. Consequently, using this assay, only ADA binding to the CDRs of the Nanobody are detected. Those ADA are considered to have neutralizing potential, although clinical relevance (i.e., ability to block binding of vWF) will be dependent on affinity and titer level and should be related to PK, PD and efficacy read-outs.

All samples scoring positive in the ADA assay, will be analyzed in alternative nAb assay. Samples scoring positive in the alternative nAb assay are titrated. The titer per sample is reported as $\log_{10}(\text{titer})$. Samples scoring negative in the alternative NAb assay are not titrated and the respective titer is reported as $<\log_{10}(\text{MRD})$ with MRD=96, i.e. $\log_{10}(\text{titer}) < 1.98$.

Subjects will be classified based on their pre-dose status (i.e. baseline visit) and treatment-emergent status. Subject classification based on alternative NAb assay is as follows:

- Pre-dose negative, TE negative: no positive samples
- Pre-dose negative, TE positive: negative baseline visit and one or more positive samples post-dose.
- Pre-dose positive, TE negative: positive baseline visit and no titer increase post-dose or all samples scoring negative post-dose
- Pre-dose positive, TE positive: positive baseline visit and titer increase post-dose
- Inconclusive: no positive samples and drug is present at levels higher than the drug tolerance characteristics of the assay
- Missing: relevant ADA samples are missing

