Subjects with no positive ADA sample will be classified as pre-dose negative, TE negative in the alternative NAb assay. In listings, samples not evaluated in the alternative NAb assay will be indicated as not analyzed (NA). In graphical presentations they will be presented as negative results at the specific sample time points.

Given the possible switch to open-label caplacizumab in case of TTP recurrence, subjects will be classified based on the ADA samples available during the DB period, and the OL period separately. For the latter subject classification, the Day 1 visit of the OL treatment period will be used as baseline visit. Patients who switch to open-label caplacizumab after having received double-blind caplacizumab treatment will be classified based on the DB period and

the overall study period, but not on the OL Caplacizumab period, as the OL Day 1 baseline visit cannot be considered a proper baseline visit for this analysis. Table 7 below provides an overview of the treatment groups for which the incidence in the different classes of the subject classification based on alternative NAb will be calculated, and the analysis periods for which this will be done.

Table 7: Overview of the treatment groups based on alternative NAb

Treatment group	DB period*	OL Caplacizumab period*	Overall study period
Placebo (no OL Caplacizumab)	X		
Caplacizumab (no OL Caplacizumab)	X (i)		
OL Caplacizumab (after Placebo)	X	X (i)	
OL Caplacizumab (after Caplacizumab)	X	Not done	X (i)
Placebo	Combination of 'Placebo (no OL Caplacizumab)' and 'OL Caplacizumab (after Placebo)'		
Caplacizumab	Combination of 'Caplacizumab (no OL Caplacizumab)' and 'OL Caplacizumab (after Caplacizumab)'		
Caplacizumab Total	Combination of 'Caplacizumab (no OL Caplacizumab)' (DB period), 'OL Caplacizumab (after Placebo)' (OL Caplacizumab period), and 'OL Caplacizumab (after Caplacizumab)' (Overall study period), as indicated by (i)		

* FU samples are included in the DB period if the patients are not switching to OL caplacizumab; in the latter case the FU sample is considered part of the OL Caplacizumab period.

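### ADA-inconclusive subjects also meet the SAP's definition of negative, and the alternative NAb default then reports them as negative

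*SAP*

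**What the plan says.** SAP 9.1.1.1 sorts subjects by bridging-assay result. The negative class is "ADA negative: no positive ADA samples at any of the sampling time points". A separate class reads "Inconclusive: no positive ADA samples and drug is present at levels higher than the drug tolerance characteristics of the assay".

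The overall classification in SAP 9.1.1.2, which combines the ADA and mADA results, has the same pair. Its double-negative class is "Pre-Ab negative – Drug-induced TE ADA negative: no positive ADA samples", and an inconclusive class follows with the same wording as in 9.1.1.1. A default is added: "Subjects classified as ADA negative based on ADA assay results will per default be classified as pre-Ab negative – Drug-induced TE ADA negative".

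SAP 9.1.3 covers the alternative NAb assay, in which only ADA-positive samples are run. Its list contains "Inconclusive: no positive samples and drug is present at levels higher than the drug tolerance characteristics of the assay". The text after the list then says: "Subjects with no positive ADA sample will be classified as pre-dose negative, TE negative in the alternative NAb assay".

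The classes are reported as numbers and percentages per category in Tables 14.3.5.1 to 14.3.5.5. They also define the groups in the tables of drug concentration, RICO, vWF:Ag and platelet response by category (14.3.5.9 to 14.3.5.20).

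**The concern.** A bridging assay can miss antibodies when enough drug is present. A subject with no positive sample and drug above tolerance has not been shown to be antibody-free, and the inconclusive class exists for such subjects. As written, the negative class has no condition on drug level, so the same subject fits both classes.

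SAP 4.5.2 requires the tables to be programmed twice, independently. Two programmers could both follow the text and produce different tables. For the alternative NAb assay there is not even a choice. The default is worded by the absence of a positive ADA sample, so a drug-masked subject is reported as having no antibodies with neutralizing potential without having been tested in that assay.

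At stake is the descriptive picture of immunogenicity, a secondary objective. The negative share would be too large. Masked subjects, who by definition have drug above tolerance, would also sit in the negative group against which drug levels and effects in antibody-positive subjects are read.

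**Working it through.** No planned figure has to be reproduced. The check is whether the written classes are mutually exclusive. Two facts decide a subject's class: whether any ADA sample is positive, and whether drug exceeds the assay's tolerance.

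| Any positive ADA sample | Drug above tolerance | ADA list (9.1.1.1) | Overall list (9.1.1.2) | Alternative NAb default (9.1.3) |
|---|---|---|---|---|
| No | No | negative | double negative | negative |
| No | Yes | negative **and** inconclusive | double negative **and** inconclusive | negative |
| Yes | No | positive | by mADA result | default does not apply |
| Yes | Yes | positive | by mADA result | default does not apply |

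The second row is the defect. In the first two lists the inconclusive condition is a subset of the negative condition, and nothing says which wins. In 9.1.3 the default settles it as negative, although that assay's own list has an inconclusive class.

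The two defaults differ. The one in 9.1.1.2 acts on subjects already classified ADA negative, so it does no harm once inconclusive takes precedence. The one in 9.1.3 depends only on having no positive sample, so it captures masked subjects whatever is decided in 9.1.1.

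**Which sample decides.** The SAP does not say at which sample drug must exceed tolerance. In the adult schedule, ADA is sampled on Day 1, at Weeks 1 and 5, at Week 9 of a full extension, at a second or subsequent recurrence visit, and at both follow-up visits. It is not sampled at the early termination visit. PK is measured at each of the on-treatment ADA visits but at neither follow-up visit. SAP 9.1.2 treats follow-up samples as wash-out. The footnotes to Tables 5 and 7 move the follow-up samples of subjects who switch to the open-label period, so a switching subject's double-blind classification has no wash-out sample.

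**Illustration.** The inputs are 132 subjects randomized 1:1 (SAP 3.1), hence 66 on caplacizumab, and 6 assumed positives, close to the 9% with drug-induced antibodies in phase II (Protocol 1.2.5): 6/66 = 9.1%. The number inconclusive, k, is an assumption. Read literally, the negative share is (66 − 6)/66 = 90.9% for every k. With inconclusive taking precedence it is (60 − k)/66. Evaluable means not inconclusive.

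| k | Negative, literal | Negative, inconclusive first | Positive, of 66 | Positive, of evaluable, 6/(66 − k) |
|---|---|---|---|---|
| 0 | 90.9% | 90.9% | 9.1% | 9.1% |
| 3 | 90.9% | 86.4% | 9.1% | 9.5% |
| 7 | 90.9% | 80.3% | 9.1% | 10.2% |
| 13 | 90.9% | 71.2% | 9.1% | 11.3% |
| 20 | 90.9% | 60.6% | 9.1% | 13.0% |

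Reclassification moves the negative share. The positive rate moves only if the denominator is changed as well.

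**The case against.** The best defence is that a separately listed, narrower class is naturally read as overriding the general one, since otherwise it would serve no purpose. That is probably what was intended in 9.1.1, and a reader should not infer that the SAP chose to count masked results as negative. The defence does not reach 9.1.3, where the default is worded without exception and contradicts the list above it.

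Protocol 3.4.7.2 refers to a dedicated bioanalytical analysis plan, which may set the tolerance and the deciding sample. That is possible, and the plan is not available here. The subject classification rules are nevertheless set in the SAP, and the 9.1.3 conflict would remain.

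The analysis is descriptive, without p-values (SAP 9.2), and Listing 16.2.11.1 shows every titer and classification. This stands and limits the importance of the point.

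Some stronger readings are not supported:

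- *The reported antibody incidence is biased downward.* The tables give percentages per category in the safety population, so moving a subject from negative to inconclusive leaves the positive rate unchanged.
- *The 10% drop-out assumption gives the number affected.* It is a sample-size assumption for the first 10 days. Subjects who stop study drug without withdrawing consent for follow-up return for both follow-up visits (Protocol 3.2.3.1), where ADA is sampled, and the SAP has a separate class for missing samples.
- *Most antibody-free caplacizumab subjects are inconclusive.* This depends on a tolerance that is not given. SAP 9.1.2 calls only the functional NAb assay insufficiently drug tolerant under treatment, while 9.1.3 uses the bridging format to detect antibodies during treatment.
- *The functional NAb rule, "Subjects with no positive NAb samples will be classified as NAb pre-dose negative, TE negative", has the same fault.* Only pre-dose and wash-out samples are run in that assay, so on-treatment masking is not the issue there.

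**Conclusion.** The point holds as a minor defect of specification. In SAP 9.1.1.1 and in the overall classification, inconclusive lies wholly within negative and no precedence is stated. In SAP 9.1.3 a stated rule gives a wrong classification: drug-masked subjects are reported as negative in an assay in which they were not tested.

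The number affected cannot be determined from the documents, and the table above only shows how the shares respond to assumed counts. What changes is the negative share and the make-up of the negative group in the by-category tables, for double-blind caplacizumab and for open-label caplacizumab alike. No efficacy result or hypothesis test depends on it.

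**What to change.** Amend SAP 9.1.1 and 9.1.3 as follows.

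1. State that inconclusive takes precedence over negative in each classification.
2. Restrict the 9.1.3 default to subjects classified ADA negative, and carry ADA-inconclusive subjects as inconclusive in the alternative NAb classification. The default in 9.1.1.2 can then stay.
3. Name the deciding sample. Treat follow-up samples as wash-out, as 9.1.2 does. A subject with no positive sample and a negative follow-up sample is negative. A subject with only on-treatment samples above tolerance is inconclusive. A rule demanding a measured drug level below tolerance at follow-up would not work, because adult PK is not sampled there. Say explicitly how the double-blind period of switching subjects is classified, as it has no follow-up sample.
4. Show the inconclusive count beside the incidence in the tables. The rate among evaluable subjects may be added as a supplement.

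The cost is a few sentences and a small change to the derivation program. No new samples or assays are needed, since PK is already measured at the on-treatment ADA visits.

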9.1.2 NAb (neutralizing antibody)

The NAb assay is based on vWF-platelet interaction. As this assay is not sufficiently drug tolerant to detect NAb under treatment, only pre-dose samples (before first caplacizumab administration, i.e. baseline visit) and wash out samples (FU samples) will be analyzed.

All samples scoring positive in the ADA assay at baseline visit or FU samples will be analyzed in the NAb assay. Samples scoring positive in the NAb assay are titrated. The titer per sample is reported as $\log_{10}(\text{titer})$. Samples scoring negative in the NAb assay will be reported as $<\log_{10}(\text{MRD})$ with $\text{MRD}=2.30$ i.e. $\log_{10}(\text{titer})<0.36$. Positive samples for which no titration can be done due to insufficient sample volume will be reported as $>\log_{10}(\text{MRD})$. These positive samples (for which no titration could be done) should be plotted as $\log(\text{MRD})$ equal to 0.36 in the figure.

Subjects will be classified based on their pre-dose status (i.e. baseline visit) and treatment-emergent (TE) status. Subject classification based on NAb is as follows:

- Pre-dose negative, TE negative: no positive samples
- Pre-dose negative, TE positive: negative baseline visit and one or more positive samples post-dose
- Pre-dose positive, TE negative: positive baseline visit and no titer increase post-dose or all samples scoring negative post-dose
- Pre-dose positive, TE positive: positive baseline visit and titer increase post-dose
- Missing: relevant ADA samples are missing

Subjects with no positive NAb samples will be classified as NAb pre-dose negative, TE negative. In listings, samples not evaluated in the NAb assay will be indicated as not analyzed (NA). In graphical presentations, these samples will be presented as negative results.

Given the possible switch to OL Caplacizumab treatment in case of TTP recurrence, subjects will be classified based on the ADA samples available during the DB period, and the OL period, separately. For the latter subject classification, the Day 1 visit of the OL treatment period will be used as baseline visit. Table 6 below provides an overview of the treatment groups for which the incidence in the different classes of the subject classification based on NAb will be calculated, and the analysis periods for which this will be done.

Table 6: Overview of treatment groups in the subject classification based on NAb

Treatment group	DB period*	OL Caplacizumab period*	Overall study period
Placebo (no OL Caplacizumab)	X		
Caplacizumab (no OL Caplacizumab)	X		
OL Caplacizumab (after Placebo)		X	

CONFIDENTIAL

OL Caplacizumab (after Caplacizumab)			X
Caplacizumab Total	Combination of 'Caplacizumab (no OL Caplacizumab)' (DB period), 'OL Caplacizumab (after Placebo)' (OL Caplacizumab period), and 'OL Caplacizumab (after Caplacizumab)' (Overall study period)		

* Pre-dose and FU samples only.

9.1.3 Alternative NAb (epitope characterization; null variant assay): ADA with neutralizing potential

To detect ADA with potential neutralizing activity during treatment an alternative NAb assay will be used, consisting of the bridging ADA assay in which an altered caplacizumab molecule (i.e. caplacizumab with mutated complementary determining region [CDR] regions) is added in excess to capture all non-CDR binding ADA. Consequently, using this assay, only ADA binding to the CDRs of the Nanobody are detected. Those ADA are considered to have neutralizing potential, although clinical relevance (i.e., ability to block binding of vWF) will be dependent on affinity and titer level and should be related to PK, PD and efficacy read-outs.

All samples scoring positive in the ADA assay, will be analyzed in alternative nAb assay. Samples scoring positive in the alternative nAb assay are titrated. The titer per sample is reported as $\log_{10}(\text{titer})$. Samples scoring negative in the alternative NAb assay are not titrated and the respective titer is reported as $<\log_{10}(\text{MRD})$ with MRD=96, i.e. $\log_{10}(\text{titer}) < 1.98$.

Subjects will be classified based on their pre-dose status (i.e. baseline visit) and treatment-emergent status. Subject classification based on alternative NAb assay is as follows:

- Pre-dose negative, TE negative: no positive samples
- Pre-dose negative, TE positive: negative baseline visit and one or more positive samples post-dose.
- Pre-dose positive, TE negative: positive baseline visit and no titer increase post-dose or all samples scoring negative post-dose
- Pre-dose positive, TE positive: positive baseline visit and titer increase post-dose
- Inconclusive: no positive samples and drug is present at levels higher than the drug tolerance characteristics of the assay
- Missing: relevant ADA samples are missing

Subjects with no positive ADA sample will be classified as pre-dose negative, TE negative in the alternative NAb assay. In listings, samples not evaluated in the alternative NAb assay will be indicated as not analyzed (NA). In graphical presentations they will be presented as negative results at the specific sample time points.

Given the possible switch to open-label caplacizumab in case of TTP recurrence, subjects will be classified based on the ADA samples available during the DB period, and the OL period separately. For the latter subject classification, the Day 1 visit of the OL treatment period will be used as baseline visit. Patients who switch to open-label caplacizumab after having received double-blind caplacizumab treatment will be classified based on the DB period and

the overall study period, but not on the OL Caplacizumab period, as the OL Day 1 baseline visit cannot be considered a proper baseline visit for this analysis. Table 7 below provides an overview of the treatment groups for which the incidence in the different classes of the subject classification based on alternative NAb will be calculated, and the analysis periods for which this will be done.

Table 7: Overview of the treatment groups based on alternative NAb

Treatment group	DB period*	OL Caplacizumab period*	Overall study period
Placebo (no OL Caplacizumab)	X		
Caplacizumab (no OL Caplacizumab)	X (i)		
OL Caplacizumab (after Placebo)	X	X (i)	
OL Caplacizumab (after Caplacizumab)	X	Not done	X (i)
Placebo	Combination of 'Placebo (no OL Caplacizumab)' and 'OL Caplacizumab (after Placebo)'		
Caplacizumab	Combination of 'Caplacizumab (no OL Caplacizumab)' and 'OL Caplacizumab (after Caplacizumab)'		
Caplacizumab Total	Combination of 'Caplacizumab (no OL Caplacizumab)' (DB period), 'OL Caplacizumab (after Placebo)' (OL Caplacizumab period), and 'OL Caplacizumab (after Caplacizumab)' (Overall study period), as indicated by (i)		

* FU samples are included in the DB period if the patients are not switching to OL caplacizumab; in the latter case the FU sample is considered part of the OL Caplacizumab period.

